In a pilot study conducted in the Emergency Department, Queen Elizabeth University Hospital (20/NS/0064), the Thales High Temperature Detection (HTD) system was found to be more accurate than a tympanic thermometer (Ref) which captures Infrared radiation emitted by the tympanic membrane in the ear. (Figure 1) or forehead thermometer. Tympanic temperature measurements are typically used in the hospital setting in Scotland whereas forehead IR measurement is common in transportation and workplace settings.

[figure not shown]

Figure 1: Distribution of variance between measurements for each subject for tympanic thermometer and HTD (n = 80)

The HTD has been redesigned in response to three key findings from the pilot study:

- The relative temperature of some facial features correlated more strongly with tympanic temperature than others.
- Having an external Black Body (BB) calibration source in the scene at all times was impractical in a clinical environment
- Camera systems require to be compact and portable to be useful to clinical staff.

As a result, the HTD is now significantly reduced in size, including peripheral devices. A novel calibration solution has been designed (and patented) that not only removes the need for the black body source but allows for a more accurate temperature evaluation. In addition, facial feature detection has been integrated into the software to allow it to automatically locate the patient's head and in the near future, automatically determine the temperatures of individual facial features. This development will capture facial feature detection – not facial recognition.

[figure not shown]

Figure 2: Temperature Measurement vs Actual

Figure 2 shows that the thermometer (juniper) in forehead mode appeared to return measured temperature + an offset to estimate core. The HTD can be calibrated in the same way i.e. to use the actual forehead temperature returned from the HTD plus the same offset. For tympanic comparison, the maximum temperature returned by the HTD (probably the canthus) correlates best – but it is still likely that some post processing will be required to ensure that a direct comparison can be made.

2. Aims

The Thales HTD (High Temperature Detection) System is a thermal camera based, human temperature measurement system.

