- To establish performance of internal calibration of Thales device
- To power for a definitive Clinical Investigation to determine clinical efficacy and safety cut off with HTD

4. Study Design

Patient Identification

Two groups will be identified

1. Patients who present to the Emergency Department (ED) in QEUH will be approached either by ED nurses or clinical fellows they can approach reception staff/nurse directly for information after reading posters on the ED wall.
2. QEUH ED staff will be approached either by ED nurses or clinical fellow.

Inclusion criteria

- *Patients ≥ 16 years old with no upper age limit*
- *Patients able to read and understand English*
- *Patients able to give informed consent*
- *Patients being triaged through ED for any complaint (not necessarily COVID-19)*
- *QEUH ED staff*

Exclusion criteria

- *Patients not meeting the inclusion criteria*
- *Patients who do not have capacity to consent*
- *Patients attending ED who are fast-tracked without triage*

Consent

Participants will be given a participant information sheet (PIS v2) to read while they are in waiting to be triaged (patients) or working in the ED (staff). There will be posters displayed publicising the study, and if people are interested they can ask reception staff or a nurse for more information. The nurse or fellow will go through the PIS and provide opportunity to ask questions. Due to the circumstances there is no opportunity for patients to take the PIS away and discuss it with friends/family which would be preferred. If the patient/staff member wishes to participate, a consent form will be provided which has some statements to agree to and sign. The participant can keep a copy of the signed consent form as well as the PIS. Failure to consent will not change clinical care for patients.

The PIS will make it clear that Thales will hold a copy of the identifiable images for a maximum of 1 year. Thales will securely store and analyse visible and thermal data required for future algorithm upgrades. It is anticipated that Thales will require to hold onto both visible and thermal data long enough to be required for regulatory purposes. For example, it is anticipated that the thermal data, and associated metadata, will be required for a maximum of ten years and the visible data for a maximum of one year, after which time the data will be securely destroyed.

Study procedures

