After the participant has consented to take part, the research will take a front view with the thermal imaging camera. The following data is routinely collected at triage and a copy of the data will also be entered into the Thales electronic Case Report Form (eCRF). No patient name or personal details will be held by Thales.

- Temperature
 - Oral
 - IR Forehead
 - Ear
- History of Fever Y/N
- Age
- Ethnicity
- If they are wearing contact lenses

While desirable to have uncovered face thermal images, it is accepted that some patients may choose to wear facemasks. Patients will be asked to remove spectacles.

It is expected that the thermal imaging system will sit on a table or worktop and image patients approximately 1.5m to 2.0m away. The system will require access to a mains wall socket. The kit will remain set up in a locked room when not being used.

The system will comprise of:

- Surface Pro Tablet PC;
- Thales camera mounted on a portable tripod;
- Thermal calibration Black Body source (for calibration validation purposes only).
- MiFi internet connection
- Forehead thermometer
- Tympanic thermometer

The tablet will auto-run easy to use software allowing hospital staff to record:

- Thermal and TV image of the patient front on;
- Non-personal patient metadata:
- Patient temperature measured by existing clinical methods

The system will be simple to use and aims to minimise the disruption of the QEUH staff. Thales will have provided training of QEUH staff on how to operate the equipment and support of the equipment during the data collection activity. Training will take the form of a pdf, training video and if required a video conference call.

Follow Up

There is no follow up required – patients are only required to commit to one hospital visit when they initially present at ED and have their picture taken with the thermal imaging camera. Staff will require only to have their picture taken.

5. Withdrawal

If participants wish to withdraw their consent after the intervention (after the image has been taken) they can do so and it will not affect their clinical treatment. They may withdraw from the study at their own request and are not required to give a reason for this. They will be made aware that this will not affect their future care. Participants will be made aware that should they withdraw the data collected to date will be retained and used in the final analysis.

6. Data handling, analysis and archival

Data Handling

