All the information obtained about participants in the course of the study is confidential and will be held in accordance with the General Data Protection Regulation (GDPR 2018). Data will be entered into a custom graphical user interface (GUI). Once the images and metadata have been recorded they will be regularly and periodically encrypted and then the unencrypted images deleted from the device automatically. Encrypted data will be synced with an encrypted dropbox and then transferred to Thales secure servers. Data will be unencrypted when it reaches the secure Thales servers.

Data are stored on dedicated storage area implementing Mandatory Access Control for an explicit list of authorised users. The management of those IT resources are performed by Thales UK Ltd. Thales UK Ltd is certified against the Cyber Essential Plus scheme.

Data Analysis

Personal data will be collected and processed only for the purpose of answering the research questions. The thermal images are Personally Identifiable Information (PII) and will be retained by the company for as short a time as possible before being permanently deleted. The other data items are not PII and are low risk in terms of identifying the patient from anonymised data. Personal information will not be shared with anybody outside the study.

The feasibility study data will primarily be analysed using statistical methods looking for relationships between facial feature temperatures and patient metadata. Artificial Intelligence (AI) /Convolutional Neural Network (CNN) based feature detection algorithms *may* be used to find the coordinates of the key points on the face in the visible image. The corresponding coordinates can be found with fine camera alignment and calibration. The thermal features may then be extracted for analysis along with the patient metadata. A manual feature extraction method may be used instead of the AI/CCN method if deemed more efficient for the smaller, initial dataset of 200 patients. Manual inspection of thermal images will be used to look for patterns and anomalies.

Three readings will be done per participant and comparisons done between:-

1. Tympanic vs. Thermal
2. IR vs. Thermal

A sample of size 100 will give 95% CIs for the limits of agreement of +/- 0.34 standard deviations (i.e. about a third of the standard deviation)

A sample of size 200 will give 95% CIs for the limits of agreement of +/- 0.24 standard deviations (i.e. about a quarter of the standard deviation)

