Each participant will be assigned a study identity number, for use on all trial documents and the electronic database. Other than the identifiable images, no personally identifiable information will be stored. The identifiable images will be deleted as soon as possible – but certainly within 1 year. However, for the avoidance of doubt, all other unidentifiable images will be stored for up to 10 years. Very limited research data is required and this will be stored using the study identity number. Thales will not hold a key. The site will hold the key within the local site file until to link the images and the data, and this will be archived locally.

All data will be automatically encrypted shortly after acquisition. Original, unencrypted images will be securely deleted. All encrypted data will be held on the password protected tablet PC during the trial for backup purposes. All encrypted data will be synced with an encrypted

Thales Thermography Study Protocol: V2 09.09.20

dropbox. The encrypted data will be placed on secure Thales servers and stored within password protected folders. Data will then be unencrypted for analysis.

Personal data will be stored for 10 years following the end of the study, so that the Chief Investigator may provide participants with a summary of the research (should they wish to receive a copy). Data generated as a result of this study will be available for inspection on request by NHS Greater Glasgow & Clyde, the REC, local R&D Departments and the regulatory authorities.

9. Indemnity

Insurance and indemnity for trial participants and trial staff is covered within the NHS Indemnity Arrangements for clinical negligence claims in the NHS. There are no special compensation arrangements, but trial participants may have recourse through the NHS complaints procedures.

10. Dissemination of results and publication

If results are encouraging the aim would then be to undertake a clinical investigation in order to get CE marking for use in a clinical setting - with a fever "yes/no" result. Nonetheless preliminary results may be publishable in a peer reviewed journal.

11. References

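### If HTD temperatures are extracted by hand, nothing in the stated data flow keeps the comparator readings from the person extracting them, so agreement could look better than it is

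*Protocol*

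**What the plan says.** **How the HTD value is obtained.** Section 2 lists a forehead and a head temperature from the HTD system among the recorded measurements. The background text says the software already finds the head automatically, but that it will only "in the near future, automatically determine the temperatures of individual facial features". For the tympanic comparison it points to the highest temperature the HTD returns, and it expects some further processing, not defined, before a direct comparison is possible. Section 6 (Data Analysis) makes the AI/CNN route optional and adds: "A manual feature extraction method may be used instead of the AI/CCN method if deemed more efficient". It then says: "The thermal features may then be extracted for analysis along with the patient metadata".

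**Where the comparator values are.** Section 4 (Study procedures) puts oral, IR forehead and ear temperatures into the manufacturer's eCRF. The tablet that stores the thermal and visible images also records "Patient temperature measured by existing clinical methods". Section 6 (Data Handling) sends images and metadata together: "Data will be unencrypted when it reaches the secure Thales servers". Section 8 gives the purpose: "Data will then be unencrypted for analysis".

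**What is not stated.** The protocol does not say who extracts features, whether that person is masked to the comparator temperatures, or how a region is to be placed.

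**The concern.** In a method-comparison study the index reading should be made without knowledge of the reference. A region drawn by hand on a thermal image involves judgement, image by image. An extractor who knows the tympanic or forehead value can drift, without intending to, towards the placement that matches it. Choosing in advance which HTD output to analyse does not prevent this.

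Both planned summaries would be affected: the mean difference moves towards zero and the limits of agreement narrow. Sections 2 and 10 make a clinical investigation for CE marking depend on encouraging results, and section 3 lists powering that investigation as an objective. An SD that is too small would therefore be carried forward into its sample size.

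**Working it through.** **1. The plan's own precision figure.** The half-width of the 95% CI for a limit of agreement, in SD units, is 1.96 × √(3/n) (end of Data Analysis, section 6).

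- n = 100: 1.96 × √0.03 = 0.34
- n = 200: 1.96 × √0.015 = 0.24

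Both stated figures reproduce. They describe sampling error only. A systematic shift in how regions are placed is outside them.

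**2. The route to unmasked reading.** Manual extraction is permitted (section 6). Comparator temperature and image are captured on one tablet (section 4). Both travel to the same servers and are decrypted there for analysis (sections 6 and 8). Features are to be analysed with the metadata (section 6). Followed as written, nothing hides the comparator from a manual extractor.

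**3. Possible size.** The inputs are assumptions, because the documents give neither an SD of differences nor a spread between placements:

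- total SD of the HTD-minus-comparator difference under masking: 0.30 °C;
- part due to region placement, w: 0.10, 0.15 or 0.20 °C, leaving √(0.30² − w²) = 0.283, 0.260 or 0.224 °C for the rest;
- two plausible placements per image, with the one closer to the comparator always kept (worst case).

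Simulation results; half-width of the limits = 1.96 × SD:

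| True bias (°C) | w (°C) | Apparent bias (°C) | Apparent SD (°C) | Half-width (°C) |
|---|---|---|---|---|
| 0 | masked | 0 | 0.300 | 0.59 |
| 0 | 0.10 | 0 | 0.252 | 0.49 |
| 0 | 0.15 | 0 | 0.228 | 0.45 |
| 0 | 0.20 | 0 | 0.206 | 0.40 |
| 0.30 | masked | 0.30 | 0.300 | 0.59 |
| 0.30 | 0.10 | 0.261 | 0.270 | 0.53 |
| 0.30 | 0.15 | 0.240 | 0.255 | 0.50 |
| 0.30 | 0.20 | 0.216 | 0.240 | 0.47 |

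The SD is 16–31% too small at zero bias (1 − 0.252/0.30 and 1 − 0.206/0.30) and 10–20% too small with a bias of 0.30 °C. At zero bias the share of readings within ±0.2 °C rises from 50% to 62–71%.

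**4. Partial selection.** If only 25% of images were steered (also an assumption), the zero-bias SD is 0.289–0.280 °C, which is 4–7% too small.

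**5. Consequence for the next study.** Suppose the later study were sized by the plan's formula for a fixed half-width h. Then n = 3 × (1.96 × SD / h)², so n scales with SD². The planned size would be (0.252/0.30)² = 71% down to (0.206/0.30)² = 47% of what is needed at zero bias. With the 0.30 °C bias it would be (0.270/0.30)² = 81% down to (0.240/0.30)² = 64%. These are again worst-case figures.

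**The case against.** The strongest reply is that the manual option is not tied to the primary comparison. It closes a paragraph about relating facial features to metadata, which reads as exploratory, and the two agreement comparisons are introduced afterwards. Section 2 lists the HTD readings as coming from the system. This stands, and it is why the point is conditional. But the same section names no other source for the thermal value and does not exclude a hand-extracted one.

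Second, a maximum over the face leaves little room for placement. This also stands: the tympanic comparison is less exposed. It is not wholly protected, since the undefined post-processing is a further choice that could be made with the comparator in view.

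Third, section 8 says the manufacturer holds no key and that the site keeps one linking images and data. Read with the archival text in section 6, this is an identity key for confidentiality. It does not separate image from comparator, because the tablet and the transfer keep them together.

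Fourth, masking is often left to an SAP or a reading manual. Here, though, the protocol itself fixes the data flow, and a later document cannot restore masking once the two have been viewed together.

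A reader might also infer that the manufacturer itself makes the manual readings. No sentence says so: "Thales will securely store and analyse visible and thermal data required for future algorithm upgrades" concerns algorithm development. Nor do the documents plan to exclude images. They plan only an inspection for patterns and anomalies.

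**Conclusion.** The point holds in conditional form. The protocol permits manual feature extraction and keeps comparator temperatures with the images up to and including analysis, with no masking. If a hand-extracted value supplies an HTD reading in the agreement analysis, chiefly the forehead one, the bias and limits of agreement are open to distortion, and the direction is towards better agreement.

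The size is not known. The figures above rest on an assumed SD, an assumed placement spread and consistent selection of the closer placement. The larger reduction in SD (to 0.25–0.21 °C) applies only at zero bias and should not be quoted beside the shrinkage of a 0.30 °C bias, where the SD is 0.27–0.24 °C.

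It would go too far to infer that the study's conclusion would be reversed. In this illustration the narrowed limits (±0.40 °C at best) still lie outside ±0.2 °C, and the reduced bias (0.22 °C at the lowest) stays above 0.2 °C. It would also go too far to say that HTD agreement as a whole is compromised, since the tympanic comparison is less exposed. The practical risk is a favourable impression and an understated SD for the next study.

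**What to change.** Add to section 6 (Data Analysis) that:

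- every HTD temperature used in the agreement comparisons is either the automatic system output or is extracted from files with the tympanic, forehead and oral temperatures and the fever history withheld;
- any post-processing rule, and any decision to set an image aside, is made under the same masking;
- the HTD dataset is locked before it is linked to the comparator readings by study ID.

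The study ID already exists, so the change amounts to a separate export of the comparator fields and one lock step. The downside is small: the manufacturer must wait for linkage before tuning its algorithms on these data.
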